7.2.1 Secondary Objective Analyses (if applicable)

Further exploratory analyses will investigate whether stress-induced changes in learning and memory are associated with the magnitude of the stress-induced cortisol and adrenergic response by using these measures as covariates in the above analyses. We hypothesize that larger stress-induced increases in cortisol are associated with stronger benefits for statistical learning and impairments for episodic encoding. In the fMRI study, we will test whether stress exposure modulates stimulus-evoked and ITI-evoked pupil dilation, processes previously been shown to be modulated by stress exposure and associated with subsequent episodic memory (Henckens et al 2009; Qin et al 2012), although the role of pupil reactivity in statistical learning is unclear.

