3.3 Objectives

The objective of this study is to leverage novel behavioral and neuroimaging assays to determine how stress modulates distinct hippocampal learning processes in humans. Using a between-subjects design, we will investigate whether exposure to a mild laboratory stressor changes the formation of different types of memories; specifically, storing individual experiences (episodic encoding) and learning environmental regularities (statistical learning). Our central hypothesis is that stress will modulate hippocampal responses and connectivity to enhance statistical learning while impairing episodic encoding. The following specific aims will be addressed:

Aim 1. Characterize how acute stress affects the relative expression of statistical learning and episodic encoding.

Aim 2. Identify the neural mechanisms by which stress influences statistical learning and episodic encoding.

As a secondary objective, we will determine whether individual variability in the magnitude of the stress response influences the effects of stress on hippocampal learning.

Protocol Number [Protocol Number](#) Version Date and Version #

4 Study Design

Overview

The in-lab experiments will consist of two testing sessions on two consecutive days. Sessions will occur between 12:00-6:00pm to account for circadian fluctuations in cortisol (Lupien et al., 2007). On Day 1, participants will be exposed to a stress or control manipulation followed by a learning task. On Day 2, participants will be tested for their memory. At the end of the experiment, the experimenter will answer any remaining questions from the participant.

Participants will provide multiple salivary samples over the course of the experiment. Saliva will be collected using salivettes, which participants will be instructed to hold under their tongue for two minutes. These will be stored in sterile tubes in a -20 freezer. The samples will be exclusively analyzed for cortisol and alpha-amylase concentrations.

Both behavioral and fMRI studies will follow the same overall design, which is described below.

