4.2 Outcome Variables/Endpoints

Behavioral measures of learning: during the learning task, participants will make responses to the stimuli viewed on the computer screen. Responses will be analyzed to assess learning-related effects (e.g., faster responses for predictable displays).

Behavioral measures of memory: during the memory task, participants will make judgments about whether they remember specific displays or sequences of displays. We will analyze their accuracy on these tasks to create a memory score.

Cortisol response: Saliva samples will be collected at multiple timepoints throughout the experiment. These samples will be assayed to quantify levels of the stress hormone cortisol, which will be used to assess basal levels per participant and determine the efficacy of our stress induction.

Alpha-amylase response: Saliva samples will be collected at multiple timepoints throughout the experiment. These samples will be assayed to quantify levels of salivary alpha-amylase, a proxy for the adrenergic stress response. These will be used to assess basal levels per participant and determine the efficacy of our stress induction.

Subjective measures of stress: Subjective ratings of stress will be collected after the stress manipulation to assess individual differences in subjective stress responses.

fMRI BOLD response: For the fMRI experiment, we will be collecting BOLD data for the entire brain during the learning task. Various analyses will be performed on these data to assess neural correlates related to learning and memory.

Gaze/pupil dilation: For the fMRI experiment, we may also collect eye-tracking data during the learning task. Various analyses will be performed on these data to assess proxies for noradrenergic responses and signals related to learning and memory.

Questionnaire responses: Questionnaires such as the Perceived Stress Scale will be scored to assess participants' individual differences in baseline stress levels and determine whether they influence learning and interact with acute stress.

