4.2.2 Secondary and Exploratory Outcome Variables/Endpoints (if applicable)

To assess whether individual differences in the magnitude of the stress response predict the effect of stress on memory, we will leverage both objective and subjective measures of the stress response. We will test whether the change in cortisol and alpha-amylase from pre- to post-stress induction and subjective measures of stress – in addition to baseline levels of stress as measured through questionnaire data – predict the influence of acute stress on our neural and behavioral measures of learning and memory. We will also assess whether anticipatory noradrenergic responses (via pupil dilation) differ with stress and correspond to facilitated learning.

5 Study Participants

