6.1 Study Procedures

Each experiment will take place across two sessions on two consecutive days. The two sessions will occur 24h apart and will each be conducted between 12-6pm to control for circadian fluctuations in cortisol levels (Lupien et al 2007). Participants will be recruited via the procedures described in 5.4.

On Day 1, participants will be greeted by a member of the study personnel and consent will be obtained. Participants will be randomly assigned to either the Stress group or the Control group. Participants will become acclimated to the study environment and complete intake questionnaires. Participants will then provide a saliva sample (#1) to determine basal levels of cortisol and alpha-amylase. Participants randomly assigned to the Stress group will then undergo the cold pressor test (arm submerged in 0-2C cold water for 3 minutes), while participants in the Control group will have their arm submerged in warm water (37-40 C) for 3 minutes. Participants in the Stress group may be informed that they will be video recorded during the task. Then, a second saliva sample (#2) will be acquired.

Participants will then undergo a brief rest period to allow for the cortisol stress response to emerge (Shields et al., 2017). The duration of this rest period may differ across experiments so that we can assess the influence on the delay between stress and learning on subsequent outcomes. Participants will sit silently or watch a neutral video during this period. If participants are enrolled in the MRI study, we may collect anatomical and resting state fMRI scans during this time.

Following this rest period, an additional saliva sample will be taken (#3), and participants will complete the behavioral learning task. Participants will be exposed to a series of displays on the computer screen (see section 4) and be asked to make responses on a computer interface. After they complete the behavioral task, they will give one more saliva sample (#4), and then be dismissed for Day 1.

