7.1 Sample Size Considerations

For the behavioral studies, we aim for an $N = 46$ per condition. This is consistent with the sample size of the study on which this behavioral experiment is based (Sherman & [name], 2020).

To determine the sample size for the fMRI study, we conducted power analyses based on our previous work demonstrating evidence of statistical learning in the hippocampus (Sherman et al., 2020). These results indicate that we would need $N = 40$ participants per group to detect neural effects ($d = .45$, 80% power). Thus, we will recruit 80 participants and randomly assign them to Stress ($N = 40$) or No Stress ($N = 40$) conditions.

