7.2 Planned Analyses

We will test the hypotheses that: (1) stress enhances statistical learning (rmANOVA; facilitated reaction time for predictable items during learning in the Stress vs No Stress group); (2) stress enhances retention of statistical learning (*t*-test; better discrimination of *AB* category pairs in the Stress vs No Stress group); and (3) stress impairs episodic memory (*t*-test; overall lower exemplar recognition memory in the Stress vs No Stress group). Although there may be a global effect of worse episodic memory in the Stress group, we expect such deficits to be driven in part by an interaction with category type (*A*, *B*, or *X*). That is, if Stress potentiates statistical learning, these participants would quickly learn to anticipate the *B* category while viewing the preceding *A* category item. Thus, rather than focusing on encoding the *A* category item, they would be predicting the *B* category, leading to greater competition between encoding and statistical learning (rmANOVA; greater deficits in memory for *A* relative to *X* items in the Stress group).

For the fMRI experiment, we will investigate the neural mechanisms underlying stress effects on different forms of learning using a combination of *connectivity*, *multivariate*, and *univariate* approaches. Specifically, we will test the working hypothesis that stress will have opposite effects on neural processes supporting episodic encoding and statistical learning. Based on rodent models, we hypothesize that stress will facilitate the function of subregions and connections associated with the monosynaptic pathway (MSP) while impairing or sparing the function of the trisynaptic pathway (TSP).

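### Section 7.2.1 enters hormone response only as a covariate, so it yields one slope pooled over Stress and Control and does not test whether the association differs by group

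*Combined protocol and SAP*

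**What the plan says.** The question is put in three places.

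- Section 3.3 gives it as the secondary objective: "we will determine whether individual variability in the magnitude of the stress response influences the effects of stress on hippocampal learning".
- Section 4.2.2 will test whether pre-to-post change in cortisol and alpha-amylase, subjective stress and baseline questionnaire scores "predict the influence of acute stress on our neural and behavioral measures of learning and memory".
- Section 7.2.1 adds a direction: "larger stress-induced increases in cortisol are associated with stronger benefits for statistical learning and impairments for episodic encoding".

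The only method stated for the two hormones is in section 7.2.1, which labels the work exploratory. It will examine whether effects on the outcomes "are associated with the magnitude of the stress-induced cortisol and adrenergic response by using these measures as covariates in the above analyses". The analyses it refers back to are the Stress versus No Stress t-tests, repeated-measures ANOVAs and fMRI group comparisons of section 7.2.

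Two interactions are named elsewhere, and neither is this one. Section 4.2 says of the questionnaire scores that the aim is to "determine whether they influence learning and interact with acute stress". Section 7.2 says of episodic memory that "we expect such deficits to be driven in part by an interaction with category type", where the category types are the A, B and X items.

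**The concern.** The objective is about how the effect of stress varies with response size. A covariate added to a two-group comparison, with no product term, gives a single slope for everyone. That slope mixes cold-water participants, whose hormone change reflects the stressor, with warm-water participants, whose change does not.

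Two readings of the result would then be open, and neither follows from the pooled slope alone. A weak or null slope could be taken to mean that response size is irrelevant, when a real association under stress has been diluted. A positive slope could be taken as specific to stress, when the same value can arise from a link in Control only. If the model is left open, the choice between a pooled slope, a within-Stress slope and an interaction can also be made after the data are seen.

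**Working it through.** **Text check.** Section 4.2.2 states an aim and no model. The interaction in section 4.2 is written for questionnaires, and the one in section 7.2 is with item category. No Group × hormone term, group-specific slope or check of equal slopes is stated for cortisol or alpha-amylase.

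**Inputs from the plan.** Section 7.1 gives 46 per condition for the behavioural studies and 40 per group for fMRI ("we will recruit 80 participants and randomly assign them to Stress"), while section 5.2 gives N = 100 for fMRI, that is, 50 per group if split equally. The plan gives no power figure for this analysis, so there is none to reproduce. It gives no hormone SDs, slopes or significance level.

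**Assumed.** Residual SD 1; SD of hormone change in Stress 1; mean shift between groups 1 SD; direct group effect 0.1; two-sided 0.05. c = Control SD / Stress SD, taken as 1, 0.5 and 0.25.

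**Algebra.** With a group term and one covariate, least squares gives

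b_pooled = w·b_Stress + (1 − w)·b_Control, with w = SSx_Stress / (SSx_Stress + SSx_Control) = 1/(1 + c²) for equal group sizes.

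- Common slope: b_pooled equals that slope at every c.
- Stress-only slope b: b_pooled = b/(1 + c²). For b = 0.4 this is 0.4/2 = 0.20, 0.4/1.25 = 0.32 and 0.4/1.0625 = 0.376 at c = 1, 0.5 and 0.25, a loss of 50%, 20% and 6%.
- Control-only slope 0.4: b_pooled = 0.4·c²/(1 + c²), which is 0.20 at c = 1 and 0.08 at c = 0.5.

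**Simulation, 46 per group** (20,000 trials per setting; percentage significant):

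| Slope in Stress, Control | c | Expected pooled slope | Pooled | Group × change | Stress slope alone |
|---|---|---|---|---|---|
| 0.4, 0 | 1 | 0.20 | 44.8% | 45.6% | 73.2% |
| 0.4, 0 | 0.5 | 0.32 | 64.6% | 21.6% | 73.7% |
| 0.4, 0 | 0.25 | 0.376 | 72.1% | 9.8% | 73.8% |
| 0, 0.4 | 1 | 0.20 | 45.2% | 46.0% | 5.0% |
| 0, 0.4 | 0.5 | 0.08 | 9.2% | 22.0% | 5.1% |
| 0.4, 0.4 | 1 | 0.40 | 96.1% | 5.1% | 73.6% |
| 0.4, 0.4 | 0.5 | 0.40 | 83.4% | 5.1% | 73.5% |

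The first and fourth rows show the ambiguity: at equal spread, a Stress-only link and a Control-only link give the same pooled slope and the same chance of significance. The sign of the Group × change term separates them.

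**Range.** For a Stress-only slope of 0.2 to 0.6, the pooled test is significant in 15.5% to 76.0% at c = 1 and 22.0% to 92.0% at c = 0.5. The Group × change term reaches 15.2% to 78.7% and 9.3% to 41.9%.

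**fMRI.** For a Stress-only slope of 0.4 at c = 1, pooled and Group × change give 39.9% and 39.8% at 40 per group, and 49.0% and 49.8% at 50 per group.

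**Repeated-measures form.** With A and X scores correlated 0.5 (assumed) and a slope of −0.4 on A items under Stress only, the pooled item type × change term is −0.200, −0.317 and −0.376 at c = 1, 0.5 and 0.25. The dilution is the same. Group × item type × change is significant in 45.3%, 21.9% and 9.8%.

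**Precision.** At 46 per group the 95% interval half-width is about 0.30 for the Stress slope, and 0.43, 0.67 and 1.24 for Group × change at c = 1, 0.5 and 0.25.

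**The case against.** The strongest reply is that section 7.2.1 does not exclude a product term. Section 4.2.2 speaks of predicting the influence of stress for hormones and questionnaires together, so an interaction may well be intended. That stands as a reading of intent, but the method sentence still names covariates only, and the interaction wording in section 4.2 is attached to questionnaires.

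It is also fair that section 7.2.1 speaks of association. If the question is dose-response with a common slope, the pooled covariate is apt and is the stronger test (96.1% against 73.6% for the Stress slope alone at c = 1). This is why the pooled slope should stay.

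Three stronger readings are tempting, and the documents do not support them.

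- A reader might infer that the planned analysis is wrong or badly underpowered. The loss is large only if Control varies about as much as Stress, and the documents give no spreads.
- A reader might infer that a within-Stress slope adjusted for sample #1 should become the main estimate. By itself that slope does not show specificity to stress. If change and baseline correlate at −0.3 to −0.5 (assumed), its power falls to 69% to 60%, against 64.6% and 72.1% for the planned covariate at c = 0.5 and 0.25. It is a trade-off, not a correction.
- A reader might infer that the hormone-adjusted group coefficient will be reported as the stress effect. Hormone change is measured after assignment, so adjusting for it does change that coefficient's meaning, but no section says it will be read that way.

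Finally, no section says that a null slope will be taken as irrelevance or a positive one as stress-specific. The risk lies in later interpretation and is not a stated plan.

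**Conclusion.** The concern holds as a gap between the secondary objective and its one stated method. Followed literally, section 7.2.1 gives a spread-weighted average of two slopes. That average answers a dose-response question if the slopes are equal. It does not test whether they are equal, and it understates a Stress-only association by the factor 1/(1 + c²).

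The algebra needs only equal group sizes and the literal ANCOVA reading. The significance percentages rest wholly on assumed slopes, spreads and residual SD. The practical size is unknown because c is unknown: half the association is lost at c = 1, and little at c = 0.25.

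Severity is minor. The analysis is exploratory, no sample size or decision rests on it, and the Stress versus No Stress comparisons in section 7.2 do not depend on it.

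**What to change.** In section 7.2.1, keep the pooled covariate slope and add wording to this effect:

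> For each outcome we will also fit a model with a Group × hormone-change term (Group × item type × change in the repeated-measures ANOVAs) and report the slope in each group, and their difference, with 95% confidence intervals. These analyses are exploratory and associational. Any statement that an association is specific to stress will rest on the interaction term and not on the pooled slope. A non-significant pooled slope will not be read as showing that response size is irrelevant.

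No estimate needs to be ranked as the main one. Adjustment for sample #1, which section 6.1 collects before the water exposure ("Participants will then provide a saliva sample (#1) to determine basal levels of cortisol and alpha-amylase"), is optional. So is naming which later sample counts as post-induction.

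The cost is wording only, with the same data and software. The drawback is imprecision. With a Stress-only slope of 0.4 and 46 per group, the interaction has about 46%, 22% or 10% power at c = 1, 0.5 or 0.25, which is no better than the pooled slope. If the slope is common, the interaction is expected to be null and the pooled slope carries the information. The intervals should therefore be reported and read, not only the p-values.

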7.2.2 Analysis of Subject Characteristics (if applicable)

N/A

Interim Analysis (if applicable)

N/A

7.3 Data Relevance

By examining differences in behavioral and neural measures of hippocampal learning as a function of acute stress exposure, we can test our hypothesis that stress has distinct effects on different forms of hippocampal learning.

7.4 Data Coding

N/A

7.5 Data Analysis Tools

Behavioral data will be analyzed using R. fMRI data will be analyzed using a combination of FSL, AFNI and Python.

7.6 Data Monitoring

The PIs are responsible for monitoring the data, assuring protocol compliance, and conducting quarterly safety reviews.

7.7 Handling of Missing Data

All data will be collected and stored electronically. Data will be missing only in the case of a technological failure (e.g., a computer error). Participants with incomplete datasets will be excluded from the analyses and replaced.

8 Data/Specimen Handling and Record Keeping

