2.2 Risks

Cold pressor test. The Cold Pressor Test (CPT) procedure has been used successfully with both children and adults without reported adverse effects (Von Baeyer et al., 2005; Kowalczyk et al., 2006; Siegrist et al., 2006; Silverthorn and Michael, 2013; [name] et al 2017a,b; [name] et al 2019). Participants may experience some discomfort during this task (submerging their hand in a bucket of water). Participants will be able to withdraw from the experiment at any time without loss of compensation (prorated to the length of participation), and will have time to rest after completion of the CPT. Participants will be given a paper towel to wipe their arm after the stressor is over, and they will be given time to rest.

MRI environment. There are no known risks in the use of MRI per se and 3-T scanners are FDA-approved for all ages. However, there are some potential areas of concern. The first is the possibility of the static magnetic field attracting ferromagnetic objects toward the bore, which includes internal devices. The second is the loud noise made by the gradients during imaging. Finally, participants may feel dizzy, get an upset stomach, have a metallic taste, or feel tingling sensations or muscle twitches. These concerns exist for all MRI studies and routine exams and are not increased by the proposed research.

All studies will follow guidelines set by the FDA with regard to specific absorption ratio, limits on gradient slew rate (dB/dt), and acoustic noise. We will use a 3-T scanner that conforms to FDA safety guidelines. Such scanners are available for research and clinical studies at most major medical centers and research universities and have been used for a number of years. Safety procedures will be rigorously enforced. Members of the research team receive intensive safety training and periodic re-training.

Subjects will be screened for contraindications to scanning, including moderate or severe claustrophobia, and a history or possible history of intra-ocular, intracranial, intrathorax, or intra-abdominal metal or cardiac pacemakers. Although there are no known risks to a fetus, if the participant is female and there is any chance they could be pregnant, the safety concerns will be explained to the participant and they will be excluded.

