4.2.1 Primary Outcome Variables/Endpoints

To characterize how acute stress affects the relative expression of different kinds of memory, we will measure statistical learning and episodic memory. Statistical learning will be assessed using responses/response times during the learning task, as well as from memory tests (see above). Episodic memory will be assessed by recognition memory performance. We hypothesize that measures of statistical learning will be enhanced following acute stress (as measured, e.g., by greater response time benefits during learning) and that measures of episodic memory (e.g., later recognition) will be diminished following acute stress.

To identify the neural mechanisms by which stress influences these different kinds of memory, we will focus on hippocampal responses measured during fMRI scanning. We hypothesize that measures of functional connectivity between hippocampal subregions CA1 and CA3 will be lower following acute stress (consistent with poorer episodic memory),

Protocol Number [Protocol Number](#) Version Date and Version #

whereas functional connectivity between subregion CA1 and the entorhinal cortex will be higher following acute stress (consistent with better statistical learning).

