6.5 Withdrawal Procedures

Participants who withdraw from the study before completion will be given the opportunity to ask questions about the study. The data collected from these participants will not be analyzed.

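### Sections 6.5 and 7.7 drop the whole participant, so Day 1 primary outcomes go unanalysed when someone misses Day 2, and Stress is compared with Control in completers only

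*Combined protocol and SAP*

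**What the plan says.** Two rules govern incomplete participants.

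- Section 7.7 (Handling of Missing Data): "Participants with incomplete datasets will be excluded from the analyses and replaced". Its premise is: "Data will be missing only in the case of a technological failure (e.g., a computer error").
- Section 6.5 (Withdrawal Procedures), on people who withdraw before completion: "The data collected from these participants will not be analyzed".

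Withdrawal is open to everyone. Section 2.2 says: "Participants will be able to withdraw from the experiment at any time without loss of compensation", with payment prorated to time taken part.

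The primary outcomes in 4.2.1 come from both days.

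- **Day 1, behaviour:** "Statistical learning will be assessed using responses/response times during the learning task". Memory tests also contribute to this construct. Section 6.1 places the task on Day 1, after the stressor and rest period: "an additional saliva sample will be taken (#3), and participants will complete the behavioral learning task".
- **Day 1, fMRI:** the hypothesis is that "measures of functional connectivity between hippocampal subregions CA1 and CA3 will be lower following acute stress", and that CA1-entorhinal connectivity will be higher. On timing, 4.2 says "we will be collecting BOLD data for the entire brain during the learning task". The Visit Schedule Table marks scanning at Visit 1 only.
- **Day 2:** the memory tests, including recognition memory, 24 hours later (6.1).

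Section 7 defines no analysis set per outcome and plans no reporting of losses by group.

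**The concern.** A participant who completes the stressor, the learning task and, where applicable, the scan, but misses Day 2, has either withdrawn (6.5) or has an incomplete dataset (7.7). Either way, everything they contributed is set aside, including primary outcomes that were fully observed.

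Two things are at stake. First, valid primary data are discarded for no analytic reason. Second, Stress and Control are compared among those who returned. Replacing leavers restores the planned number but not the groups as assigned. The groups have different experiences (ice water, possibly with video recording, versus warm water) and assignment is unblinded (6.2), so differential loss is plausible, though nothing in the documents shows it. Without losses reported by group, a reader cannot tell.

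The online studies have no assigned groups and are outside this point.

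**Working it through.** **1. Which planned analyses need Day 2 data (section 7.2)**

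| Analysis | Needs a Day 2 score? |
|---|---|
| Hypothesis 1: reaction time during learning | No |
| Background connectivity, CA1-entorhinal and CA1-CA2/3/DG | No |
| Classifier evidence for the predicted category | No |
| Hypothesis 2: category-pair discrimination | Yes |
| Hypothesis 3: recognition memory, and its interaction with category type | Yes |
| Subsequent-memory contrast | Yes |
| Connectome model predicting memory | Yes |

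For the first three rows the exclusion is avoidable; for the others it is not. Classifier evidence is a planned analysis but is not listed as primary in 4.2.1.

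**2. Inputs**

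The plan gives no loss rate, so it has no figure of its own on this point to reproduce. The targets are 46 per group (behavioural, 7.1), 40 per group (fMRI, 7.1) and, if the fMRI N is 100 (5.2) split equally, 50 per group. All loss rates and correlations below are assumptions.

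**3. Day 1 datasets left unanalysed**

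With non-return q in both groups and recruitment continuing until n complete per group, the number is 2n·q/(1−q).

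| n per group | q = 5% | q = 10% |
|---|---|---|
| 46 | 92 × 0.05/0.95 = 4.8 | 92 × 0.10/0.90 = 10.2 |
| 40 | 80 × 0.05/0.95 = 4.2 | 80 × 0.10/0.90 = 8.9 |
| 50 | 100 × 0.05/0.95 = 5.3 | 100 × 0.10/0.90 = 11.1 |

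Keeping them multiplies the Day 1 standard error by √(1−q), which is 0.975 or 0.949: a reduction of 2.5% to 5%. Power is not below plan, because leavers are replaced.

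**4. Bias in the completer comparison**

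Take an outcome with SD 1 and no true group difference. Let ρ be the correlation between the outcome and a normal latent tendency to stay. Then

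bias = ρ_S·φ(z_qS)/(1−q_S) − ρ_C·φ(z_qC)/(1−q_C).

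Here φ(z_q)/(1−q) is 0.1031/0.95 = 0.1086 at 5% loss and 0.1755/0.90 = 0.1950 at 10%. The false-positive rate is from the noncentral t distribution, two-sided 5%.

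| Loss, Stress / Control | ρ | Bias (SD) | False positives, 46 per group | 40 per group |
|---|---|---|---|---|
| 5% / 0% | 0.3 | 0.3 × 0.1086 = 0.033 | 5.3% | 5.2% |
| 5% / 0% | 0.5 | 0.5 × 0.1086 = 0.054 | 5.8% | 5.7% |
| 10% / 5% | 0.3 | 0.3 × (0.1950 − 0.1086) = 0.026 | 5.2% | 5.2% |
| 10% / 5% | 0.5 | 0.5 × (0.1950 − 0.1086) = 0.043 | 5.5% | 5.4% |
| 5% / 5% | 0.5 Stress, 0.3 Control | 0.2 × 0.1086 = 0.022 | 5.1% | 5.1% |
| 5% / 5% | equal | 0 | 5.0% | 5.0% |
| 10% / 0% (extreme) | 0.5 | 0.5 × 0.1950 = 0.098 | 7.5% | 7.2% |

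These correlations are not mild. The implied gap between stayers and leavers is ρφ(z_q)/[q(1−q)]. At 5% loss that is 0.65 SD for ρ = 0.3 and 1.09 SD for ρ = 0.5.

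**5. What per-outcome analysis recovers**

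For a Day 1 outcome with loss only at Day 2, a simulation of 4 million per group (5% / 0%, ρ = 0.5) gives a completer difference of 0.055 SD and an available-case difference of 0.001 SD. This is expected, since every Day 1 value is then observed.

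It does not recover missing Day 2 scores. If k Stress scores are unobserved and differ by δ from the 46 observed, the group difference shifts by kδ/(46+k). For δ of 0.5-1 SD that is 0.02-0.04 SD at k = 2 (2 of 48) and 0.05-0.10 SD at k = 5 (5 of 51).

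**The case against.** The strongest reply is that the effect is small. Outside one extreme corner the false-positive rate stays between 5.0% and 5.8%, and power is protected by replacement. The bias inputs are harsh, and nothing in the documents supports them. Loss over a 24-hour gap may be low, and prorated payment gives people a reason to return. All of this stands, and it limits how much weight the bias argument can carry.

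Loss might differ most at the cold-water immersion itself. Someone who leaves there has no learning-task data to keep, so the change helps only with later loss. That also stands, and it is why losses should be reported with their timing.

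Section 7.7 does not define an incomplete dataset, and neither section names a Day 2 no-show, so a narrower reading of 7.7 is possible. But 6.5 is explicit for withdrawals, and 7.7 speaks of excluding and replacing participants, not missing values. Nothing elsewhere sets a per-outcome rule.

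Aim 1 concerns the relative expression of two kinds of learning, for which a common sample is coherent. This is a fair reason to keep a completer analysis. It is not a reason to withhold Day 1 data from the separate response-time and connectivity tests.

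Finally, consent wording may limit use of data after withdrawal. The consent pages are not available here, so that part of the change must remain conditional.

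**Conclusion.** The concern holds for the in-lab and fMRI studies. The text removes the whole participant, including observed primary outcomes that need no Day 2 score, and the premise that only technological failure causes missing data does not fit a two-visit design with free withdrawal.

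The discarded data follow directly from the rules whenever someone fails to return; how much is lost depends on the assumed 5-10%. The bias is conditional and probably small: zero under equal loss with equal correlation, and about 0.02-0.05 SD in the moderate scenarios. As planned, it could not be checked. The change is worth making, but the design does not fail without it.

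**What to change.** Amend 6.5 and 7.7 for the in-lab and fMRI studies.

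- **Premise and definition.** Remove the claim that only technological failure causes missing data, name Day 2 non-return, and define completeness separately for each outcome.
- **Analysis set.** Analyse each outcome by assigned group in every assigned participant who has it. Keep Day 1 response times, background connectivity and category-prediction evidence when Day 2 is missing. Restrict only the analyses that use memory scores. Do not drop behavioural data because an ancillary measure is missing.
- **Withdrawal.** Keep data collected before withdrawal where consent allows.
- **Replacement.** Additional participants may be enrolled, but without displacing those already assigned.
- **Reporting.** Give withdrawals, non-returns and exclusions by group, with reason and timing (at the stressor, later on Day 1, Day 2 not attended).
- **Sensitivity.** Present the completer analysis as a sensitivity analysis; it also supplies the common sample for Aim 1.

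The cost is slightly different samples across outcomes, a little more analysis and reporting, an IRB amendment (9.1) and a check of the consent wording. No extra participants or visits are needed. Day 2 scores of non-returners remain missing, so the loss table is still needed for the memory outcomes.
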